2.7. Potential Risks and Benefits to Subjects of Comparator HRIG

In this study, a licensed comparator HRIG, HyperRAB[®] S/D, will be used. HyperRAB[®] S/D is a plasma-derived product and therefore the same class effects are expected as listed in section 2.5. Refer to the prescribing information in [Appendix D](#).

2.8. Potential Risks and Benefits to Subjects of Rabies Vaccine

In this study, a licensed vaccine RabAvert[®] will be used. RabAvert[®] is a sterile freeze-dried vaccine obtained by growing the fixed -virus strain Flury LEP in primary cultures of chicken fibroblasts. The most common adverse reactions are injection site reactions, such as injection site erythema, induration, pain, and flu-like symptoms, such as asthenia, fatigue, fever, headache, myalgia and malaise. Refer to the prescribing information in [Appendix E](#).

2.9. The Current Study

The purpose of the current study is to obtain data required for a license application in the US. This will be achieved by comparing the safety and efficacy of BPL HRIG, administered in

conjunction with rabies vaccine in accordance with the licensed dosing schedule for post-exposure prophylaxis, with the safety and efficacy of a licensed comparator HRIG, also given in conjunction with rabies vaccine. A randomized, blinded, parallel group study design will ensure an unbiased comparison is made between treatments.

The doses of BPL HRIG and comparator HRIG to be administered in this study, of 20 IU/kg, are consistent with the licensed doses. Unlike the licensed method of administration, which requires the HRIG to be administered around the wound, in this study HRIG will be administered to the lateral thigh muscles and, if required by the volume to be administered, to the deltoid muscle. This will result in a more consistent absorption of antibody from the intramuscular compartment between subjects and therefore allow an accurate analysis of the PK of HRIG.

It is unethical to investigate the efficacy of BPL HRIG in patients exposed to rabies virus due to the almost invariably fatal nature of the disease. Therefore, in this study, PK of HRIG when given in conjunction with active rabies vaccine to healthy volunteers will be used as a surrogate marker of HRIG efficacy. The pharmacokinetic goal of rabies post-exposure prophylaxis is to achieve a serum rabies antibody titer of ≥ 0.5 IU/mL (WHO, 2007) on study Day 14. A comparison of the proportion of subjects receiving BPL HRIG who meet this important clinical endpoint, with the proportion of subjects receiving FDA-licensed comparator HRIG who meet the same endpoint, is therefore the primary objective of the trial. The aim of the study will be to demonstrate the non-inferiority of BPL HRIG with a 10% margin.

Secondary endpoints will include rabies antibody titer at days 3, 5, 7, 14 and 28, for both HRIGs (in conjunction with rabies vaccine). PK sampling will take place prior to dosing of HRIG and rabies vaccine (Day 0) at each of the timepoints at which rabies vaccine is administered (Days 3, 7, 14 and 28), with an additional PK timepoint at Day 5 to study the early response to HRIG. Additional PK timepoints at Days 49 and 140 will enable collection of a complete the PK profile. In order to compare the effects of HRIG at early timepoints before active antibody is generated in response to the rabies vaccine, the AUC_{0-7d} will be assessed. Additional secondary endpoints will be the proportion of subjects in each treatment group reaching a serum rabies antibody titer of ≥ 0.5 IU/mL and \geq the Lower Level of Quantification (LLOQ) at each timepoint. PK parameters for both treatment groups will be compared in an exploratory analysis.

As mentioned in [Section 2.3](#), a dose of 40 IU/kg was shown to interfere with the development of active immunity conferred by the vaccine¹⁶. At a dose of 20 IU/kg, as given during this study, any attenuation observed was insignificant and did not interfere materially with active immunity^{22,23}. Moreover, any attenuation was clinically insignificant since serum anti-rabies

IgG remained considerably higher than the protective titer of 0.5 IU/mL. However, as a secondary endpoint, the possible attenuation effect of BPL HRIG on the development of the host-immune response will be studied by comparing the Day 14, 28, 49 and 140 rabies antibody titer for both treatments. Any observed attenuation will be described by comparing PK parameters of HRIGs in conjunction with rabies vaccine. Although the safety of BPL HRIG is well-established from many years of marketed use, this study will assess the safety of BPL HRIG, in conjunction with rabies vaccine.

In order to maintain blinding of treatment, the study will be blinded to the subject, investigator and site staff, to reduce bias in the identification and causality assessments of adverse events and laboratory abnormalities. An unblinded pharmacist or licensed medical professional will be responsible for preparation of the correct treatments according to the randomization code. In this study, actual (rather than nominal) HRIG potency will be used to calculate the volume of HRIG to be administered. Since there will be differences in the volume of the HRIGs the nurse administrator will also be unblinded. This modified blinding technique was successfully used in a completed study comparing PK and safety of two rabies vaccine formulations, both in conjunction with licensed HRIG²⁴.

A study duration of five times the half-life of the experimental treatment is usually considered adequate to identify safety issues relating to the product. The half-life of HRIG is 3-4 weeks¹⁹, therefore study duration of 15 to 20 weeks is considered appropriate both to obtain a full PK profile and for appropriate safety follow up. A duration of 140 days (20 weeks) has therefore been selected for this study.

3. OBJECTIVES

The objectives of this study are:

1. To demonstrate non-inferiority of BPL HRIG compared to an FDA-licensed HRIG product, in terms of the proportion of subjects achieving anti-rabies antibody titer of ≥ 0.5 IU/mL at Day 14 following treatment with HRIG in conjunction with active rabies vaccine.
2. To compare the PK of BPL HRIG in conjunction with active rabies vaccine, with FDA-licensed HRIG product in conjunction with active rabies vaccine.
3. To assess whether BPL HRIG interferes with the development of the host-immune response when given simultaneously with active rabies vaccine, relative to an FDA-licensed HRIG product
4. To evaluate the safety and tolerability of BPL HRIG in comparison with FDA-licensed HRIG product.

4. STUDY DESIGN

4.1. Study Design

This will be a prospective, randomized, double-blind, parallel-group, non-inferiority, phase II/III study of the safety and effectiveness of simulated post-exposure prophylaxis with BPL HRIG with co-administration of active rabies vaccine in healthy subjects. This is intended to be a multi-center study in the US.

Subjects will be randomly assigned to one of 2 treatment groups, as follows:

Table 4: Treatment groups assigned

Treatment group name	HRIG treatment	Rabies vaccine treatment	Number of subjects
A	BPL HRIG	active rabies vaccine	81
B	comparator HRIG	active rabies vaccine	81

Prior to randomizing a participant, all screening and baseline evaluations must be completed and the participant determined to be eligible for inclusion in the study. Randomization and the baseline visit (Day 0) should occur no later than 28 days after the completion of the screening visit.

[figure not shown]
All medicinal product preparation will be performed by the unblinded pharmacist/ or licensed medical personnel using aseptic techniques and according to a standardized procedure on Day 0. The nurse administrator will quality check the calculations, and dose/treatment assignment prior to administration. Treatments on Day 0 will be administered by an unblinded nurse administrator. All study assessments and Post Day 0 treatment administration will be performed by blinded study personnel. Investigators and subjects will be blinded to treatment assignment.

Subjects will be identified by a unique five-digit number as follows: each site will be allocated a two-digit site number (e.g. Site 01, etc.) and each subject will be allocated a three-digit subject number (e.g. 001) at the Screening Visit. Each subject will be identified by the unique site and subject number combination (e.g. 01001).

4.2. Study Plan

See [Figure 1](#) .

Figure 1: Study Plan

Actual treatment by assigned Treatment Group:

A	BPL HRIG + rabies vaccine	rabies vaccine	rabies vaccine	rabies vaccine	rabies vaccine
B	comparator HRIG + rabies vaccine	rabies vaccine	rabies vaccine	rabies vaccine	rabies vaccine

4.3. Scheduled Visits

For full details of assessments performed at scheduled visits see flow chart in [Appendix G](#).

Each subject will undergo a total of 9 visits. Subjects' eligibility will be assessed at Screening (Visit 1), which can occur up to 28 days prior to dosing. Following a repeat eligibility check at Day 0 (Visit 2), eligible subjects will be randomized and dosed with the randomized treatment (BPL HRIG /vaccine or Comparator HRIG/vaccine on Day 0. Further administration of rabies vaccine, PK sampling and safety assessments will be conducted on Days 3 (Visit 3), 5 (Visit 4) (PK sampling only), 7 (Visit 5), 14 (Visit 6) and 28 (Visit 7). An additional visit for PK sampling and safety assessment will take place on Day 49 (7 weeks/Visit 8) and Day 140 (20 weeks/Visit 9). The last visit will be the End-of-Study Assessment which will take place on Day 140 (20 weeks). This visit will comprise the final PK sample and safety assessments. The end of the trial is defined as the last subject's last End-of-Study Assessment (or the date of their last data collected, if the subject has an AE at the End-of-Study Assessment that needs to be followed, see [Appendix A](#) section 4).

4.4. Endpoints

The trial's primary endpoint will be the proportion of subjects with anti-rabies antibody titer ≥ 0.5 IU/mL at 14 days following BPL HRIG + vaccine or comparator HRIG + vaccine. The primary endpoint will be designed to determine non-inferiority with a 10% margin (see [Section 8.1.1](#)).

Additional time points are included for secondary end points, including pharmacokinetic (PK) parameters of anti-rabies antibody levels in serum at time points (Days 0, 3, 5, 7, 14, 28, 49 and 140), safety and tolerability.

As the primary endpoint is assessed at Day 14, subjects who withdraw from the study after Day 14 may still be eligible for the primary analysis, if all planned assessments up to and including Day 14 were performed.

4.5. **Unscheduled Visits**

At the discretion of the investigator, subjects may return between visits as required, additional safety laboratory measures may be undertaken as required.

4.6. **Duration of Treatment**

The duration of the study for an individual participant is expected to be 24 weeks. This comprises a screening period of up to 4 weeks (28 days) followed by a treatment period of 20 weeks. The \pm 7-day allowable window on the final study visit results in a maximum study duration for any subject of 25 weeks.

4.7. **Assignment of Treatment**

The randomization code will be prepared by a statistician. Subjects will be enrolled using an interactive web response system (IWRS), which will assign each subject to a treatment group after the demographic and eligibility data have been entered into the system. The system will allow emergency UNBLINDING, the process for which will be documented.

Manual back-up procedures and instructions are provided for use in the event that the site temporarily loses access to the Internet or the online enrollment system is unavailable.

5. TRIAL POPULATION

5.1. Subject Numbers

The trial will enroll approximately 162 healthy volunteers, 81 in each treatment arm to achieve 146 evaluable subjects

Enrolled subjects who withdraw from the study will not be replaced.

5.2. Inclusion Criteria

All the following criteria must be met for the subject to be eligible:

- a) Able and willing to sign an informed consent form.
- b) Healthy male or female subjects aged 18 - 75 years inclusive.
- c) No previous exposure to rabies virus, rabies vaccine and/or rabies immunoglobulin.
- d) No significant abnormalities in hematology, biochemistry, or urinalysis according to the Principal Investigator's judgment.
- e) No significant abnormalities in ECG according to the Investigator's judgment.
- f) Females of child-bearing potential (defined from the onset of menstruation to one-year post-menopause and not surgically sterilized) who are (or become) sexually active must agree to practice contraception by using a highly effective (>98%) method for the duration of the study.
- g) Females of child-bearing potential (defined from the onset of menstruation to one-year post-menopause and not surgically sterilized) must have a negative result on a serum at screening visit and a urine HCG-based pregnancy test at Day 0.

5.3. Exclusion Criteria

Any one of the following criteria makes the subject ineligible:

- a) Female subjects who are pregnant and/or lactating.
- b) History of live virus vaccination, e.g., measles, mumps, varicella or rubella vaccine, within the last 3 months.
- c) Planned live virus vaccination, e.g., measles, mumps, varicella or rubella vaccine, within the 3 months after Day 0.
- d) History of anaphylactic or anaphylactoid hypersensitivity reactions to chicken egg; history of mild allergic reactions to chicken egg, e.g., skin rash only, is not an exclusion criterion
- e) History of hypersensitivity reaction to any of the following components of active rabies vaccine (US-FDA approved) e.g.: neomycin, bovine gelatin, trace amounts of chicken protein, chlortetracycline, and amphotericin B and in accordance with the product insert of the vaccine.

-
- f) History of life-threatening allergy, anaphylactic reaction, or systemic response to human plasma derived products.
- g) History of life-threatening allergy to blood or blood products.
- h) Fever at the time of the start of the injection (oral temperature $>38^{\circ}\text{C}$.) or acute illness at the time of the start of the injection. *
- i) History of or ongoing bleeding disorder.
- j) Previous organ transplant recipient.
- k) Ongoing immunosuppressive illness.
- l) Clinically significant illnesses including: cardiac, hepatic, renal, endocrine, neurological, hematological, neoplastic, immunological, skeletal or other) that in the opinion of the investigator, could interfere with the safety, compliance or other aspects of this study.
- m) All types of malignancies except for basal and squamous cell (scaly or plate-like) skin cancer, in-situ cervical carcinoma must be in remission for a minimum of 5 years prior to Day 0. For non-melanoma skin cancers and carcinoma in-situ of the cervix may be enrolled if treated and cured at the time of screening.
- n) Evidence of active systemic infection that requires treatment with antibiotics within 2 weeks prior to Day 0.
- o) Currently receiving or have received within the past 6 months (prior to Day 0):
- immunosuppressive drugs
 - immunomodulatory drugs
- p) Currently receiving or have received oral or IV steroids within 14 days (prior to DAY 0) or expected to require oral or IV steroids during the study.
- q) Evidence of uncontrolled hypertension (systolic blood pressure of >150 mmHg, and/or diastolic blood pressure of >100 mmHg).
- r) Heart rate >120 /min.
- s) Weight > 95.5 kg
- t) History of IgA deficiency.
- u) Is positive for any of the following at screening: serological test for HIV 1&2, HCV or HBsAg.
- v) Presence of psychiatric disorder, other mental disorder or any other medical disorder which might impair the subject's ability to give informed consent or to comply with the requirements of the study protocol.
- w) Previous enrollment in this study.

-
- x) Participation in an interventional clinical trial within 30 days prior to baseline visit (Day 0).
 - y) Evidence of alcohol abuse or history of alcohol abuse or illegal and/or legally prescribed drugs in the past 2 years.
 - z) Any other factor that, in the opinion of the investigator, would prevent the subject from complying with the requirements of the protocol.

* Subjects with fever on Day 0 may have entry to the study re-scheduled (see [Section 7.3.1](#)).

Subjects may withdraw their consent or discontinue from the study at any time (refer to [Section 9](#)).

6. INVESTIGATIONAL AND AUXILIARY MEDICINAL PRODUCTS

In this study, 'study medication' is defined as all products administered: BPL HRIG, comparator HRIG, and active rabies vaccine.

6.1. Product Presentation, Storage and Expiry

6.1.1. Investigational Medicinal Product (IMP): BPL HRIG

BPL HRIG is a liquid concentrate of rabies human immunoglobulin. BPL HRIG is obtained from blood from screened donors, who are selected from within the United States of America. BPL HRIG is manufactured, packed and labelled by the sponsor according to the requirements of FDA CFRs, Directive 2001/20/EC and Good Manufacturing Practice.

BPL HRIG is presented in 5 ml glass vials, each of which is packed in a carton. The concentration of specific IgG to Rabies virus is not less than 150 IU/mL solution for injection in nominal 500 IU vials. The actual fill volume will be printed on the vial label. The shelf-life of BPL HRIG is specified in the Investigator's Brochure. The expiry date is printed on the vial label and carton; product must not be used beyond the expiry date. Dosing for BPL HRIG will be based on the actual potency (see pharmacy manual).

Vials of BPL HRIG should be stored in the original container at 2°C to 8°C (36°F to 46°F). Storage for up to one week at 25°C (77°F) in the original container is not detrimental. DO NOT FREEZE. Store in the original vial. Keep vial in the outer carton to protect from light. The product should be brought to room or body temperature before use.

The colour can vary from colourless to pale-yellow and is either clear or slightly opalescent. Do not use solutions that are cloudy or have deposits.

Further information can be found in the Investigator's Brochure.

6.1.2. Comparator HRIG

FDA-approved HRIG comparator HyperRAB® S/D will be presented in 10 mL vials, at a nominal potency of 150 IU/mL. Dosing for HyperRAB® S/D will be based on the actual potency (see pharmacy manual).

Vials of HyperRAB® S/D should be stored at 2°C to 8°C (36°F to 46°F). DO NOT FREEZE. The expiry date is printed on the vial label; product must not be used beyond the expiry date.

Further information can be found in the approved Prescribing Information, [Appendix D](#).

6.1.3. Active Rabies Vaccine

The FDA-approved rabies vaccine, RabAvert®, is presented as a freeze-dried vaccine containing 2.5 IU of rabies antigen for reconstitution with 1 mL diluent. Each pack contains

one vial of freeze-dried vaccine, 1 disposable pre-filled syringe of sterile diluent, 1 small needle for injection and 1 long needle for reconstitution.

RabAvert® is a white, freeze-dried vaccine for reconstitution with the water for injection diluent prior to use; the reconstituted vaccine is a clear to slightly opalescent, colorless to slightly pink solution.

RabAvert should be stored protected from light at 2°C to 8°C (36°F to 46°F). After reconstitution, the guidance in the prescribing information (PI) should be followed. The vaccine may not be used after the expiration date given on the package and container.

Further information can be found in the approved Prescribing Information, [Appendix E](#).

6.2. Randomized Treatment

Subjects will be randomized to receive one of two treatments described below.

Treatment A: BPL HRIG + rabies vaccine (RabAvert®).

A 20 IU/kg dose of BPL HRIG will be given on Day 0 via IM injection. The volume to be injected will be based upon the subject's weight on Day 0 and BPL HRIG actual potency (see pharmacy manual). A maximum of 5 mL will be administered to each lateral thigh and a maximum 2.0 mL to the deltoid muscle. The gluteal muscle will not be used for IM injection due to the increased variability of absorption from this injection site and the risk of injury to the sciatic nerve.

The total volume will be split between the injection sites as follows:

Table 5: Treatment A -total volume to be split between the injection sites

Injection number	Volume to be injected	Site of injection
1	up to 5 mL depending on bodyweight	left lateral thigh muscle
2	up to 5 mL depending on bodyweight	right lateral thigh muscle
3 (if required)	up to 2 mL depending on bodyweight	left deltoid muscle

A 1.0 ml dose of active vaccine (2.5 IU/ml) will be given IM on 5 occasions: on Days 0, 3, 7, 14, and 28. On day 0, the vaccine will be administered to the right deltoid muscle. The subsequent doses of vaccine on days 3, 7, 14, and 28 may be administered to the right or the left deltoid muscle.

The vaccine dose should never be administered into the same anatomical site as the HRIG.

Treatment B: FDA-approved comparator HRIG (HyperRAB[®] S/D) + rabies vaccine (RabAvert[®])

A 20 IU/kg dose of comparator HRIG will be given on Day 0 via IM injection. The volume to be injected will be based upon the subject's weight on Day 0 and BPL HRIG actual potency (see pharmacy manual). A maximum of 5 mL will be administered to each lateral thigh and a maximum 2.0 mL to the deltoid muscle. The gluteal muscle will not be used for IM injection due to the increased variability of absorption from this injection site and the risk of injury to the sciatic nerve.

The total volume will be split between the injection sites as follows:

Table 6: Treatment B -total volume to be split between the injection sites

Injection number	Volume to be injected	Site of injection
1	Up to 5 mL depending on body weight	left lateral thigh muscle
2	up to 5 mL depending on bodyweight	right lateral thigh muscle
3 (if required)	up to 2 mL depending on bodyweight	left deltoid muscle

A 1.0 ml dose of active vaccine (2.5 IU/ml) will be given on 5 occasions: on Days 0, 3, 7, 14, and 28. On day 0, the vaccine will be administered to the right deltoid muscle. The subsequent doses of vaccine on days 3, 7, 14, and 28 may be administered to the right or the left deltoid muscle.

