6.3. Product Administration

HRIG will be drawn into 2 or 3 (as appropriate according to the calculated volume) 5.0 mL syringes and injected to the lateral thighs and, if required, the left deltoid muscle.

Vaccine will be drawn into a 1.0 mL syringe and injected to the right deltoid muscle.

The selection of HRIG products to be administered (BPL HRIG or comparator HRIG) as per the randomized treatment, the calculation of the volume to be administered, and the drawing up of the appropriate volume into syringe(s), will be performed by the unblinded pharmacist/or licensed medical personnel. The selection of products to be administered, calculation of volume to be administered, and the volume in the syringe will be checked by the unblinded nurse administrator prior to administration to the subject.

For the BPL HRIG, comparator HRIG, the following details will be recorded:

- name of product
- lot number

-
- total dose required in IU, calculated from body weight (20 IU/kg)
 - total dose required in mL, calculated from the actual potency
 - for each specified injection site, actual dose administered in mL (this should not exceed 5.0 mL for each lateral thigh muscle and 2.0 mL for the left deltoid muscle)
 - date and time of injection on Day 0

See the pharmacy manual for additional information on calculations, potency and details to be recorded. Certificates of analysis for both products will be kept in BPL files.

For the rabies vaccine, the following details will be recorded:

- name of product
- lot number
- confirmation of actual dose given in mL (this should be 1.0 ml)
- date, time, and location of injection, on Days 0, 3, 7, 14, and 28

See the pharmacy manual for additional information on details to be recorded. For any given subject, every effort must be made to use the same lot of active rabies vaccine throughout the study.

For additional details on administration of BPL and comparator HRIG using actual potency versus nominal potency refer to [Appendix F](#) and the pharmacy manual.

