APPENDIX F. – HRIG DOSING FOR CLINICAL TRIAL

The concentration of specific IgG to Rabies virus is nominally 150 IU/mL solution for injection in nominal 500 IU vials.

The recommended dose of rabies immunoglobulin is 20IU/kg of body weight

Dosing for the trial will be calculated using the actual potency versus the nominal potency.

The potency of each lot of BPL HRIG and comparator HRIG will be provided.

To calculate the Day 0 dose; used the subject's body weight to calculate the total IUs per body weight. Then use the potency per vial to calculate the volume to be administered.

Example:

*The subject weighs 75 kg, the recommended dose is 20 IU/mL, so based on subject weight the total IUs to be administered is 1500 IU. Actual potency on the vial is 230 IU/mL, $[1500 \text{ IU} \div 230 \text{ IU/mL}] = 6.5 \text{ mL}$ of product to be administered. Volume per vial is 3.4 mL, $[6.5 \div 2.17] = 2$ vials are required. ***

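### Protocol 6.2, Treatment B, calculates the comparator HRIG volume from the potency of BPL HRIG, which contradicts the 20 IU/kg comparator dose

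*Protocol*

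**What the plan says.** Protocol 6.2 describes the two arms in parallel paragraphs. Under Treatment B it reads "A 20 IU/kg dose of comparator HRIG will be given on Day 0 via IM injection. The volume to be injected will be based", and the sentence continues by naming the subject's "weight on Day 0 and BPL HRIG actual potency". The same sentence stands under Treatment A, where it is correct. It refers the reader to the pharmacy manual in both places.

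Other parts of the protocol give a different rule for the comparator:

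- Section 6.1.2, on the comparator, says that dosing for HyperRAB "S/D will be based on the actual potency". It describes the product as supplied "at a nominal potency of 150 IU/mL".
- Section 6.3 requires, for either HRIG, a record of product name, lot number and "total dose required in mL, calculated from the actual potency".
- Appendix F says "The potency of each lot of BPL HRIG and comparator HRIG will be provided", and derives the volume from the potency of the vial in use.
- Sections 2.9 and 6.6 expect the injected volumes to differ between the two products, and give this as the reason for unblinded administrators.

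For BPL HRIG, section 6.1.1 gives only a minimum: "The concentration of specific IgG to Rabies virus is not less than 150 IU/mL solution for injection".

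**The concern.** A volume in mL converts to a dose in IU through the potency of the product in the syringe. Using another product's potency gives the intended dose only if the two potencies are equal. The two adjacent Treatment B sentences therefore cannot both be followed in general, and the faulty one is a dosing instruction for the control arm of a non-inferiority trial.

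If the comparator were under-dosed, its early antibody exposure would fall and non-inferiority would be easier to show. The most exposed comparison is the secondary AUC0-7d test with its 20% margin (Protocol 10.5.3, SAP 8f), which is not described as dose-normalised. The dose-normalised comparison is exploratory (Protocol 10.5.4). Protocol 2.3 reports that 10 IU/kg was too low for good early protection. That supports the general point that early effect depends on dose, but it does not give the size of the effect between 10 and 20 IU/kg.

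**Working it through.** **Inputs**

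- Intended dose, both products: 20 IU/kg (Protocol 2.9, 6.2).
- Comparator potency, Pc: nominal 150 IU/mL (6.1.2). The actual lot value is not given.
- BPL HRIG potency, Pb: at least 150 IU/mL (6.1.1). The actual lot value is not given.
- Appendix F example: 75 kg subject, vial potency 230 IU/mL. The product is not named; using 230 for BPL HRIG is an assumption.

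**Reproducing the plan's figure**

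Volume = 20 × weight / potency. For Appendix F, 20 × 75 = 1500 IU and 1500 / 230 = 6.52 mL, which agrees with the printed 6.5 mL.

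**Literal Treatment B rule**

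Volume = 20 × weight / Pb. Dose delivered per kg = volume × Pc / weight = 20 × Pc / Pb.

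With the comparator held at 150 IU/mL:

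| Pb (IU/mL) | 20 × 150 / Pb (IU/kg) |
|---|---|
| 150 (minimum) | 20.0 |
| 190 (midpoint) | 15.8 |
| 230 (Appendix F example) | 13.0 |

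With BPL HRIG held at 230 IU/mL and the comparator varied:

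| Pc (IU/mL) | 20 × Pc / 230 (IU/kg) |
|---|---|
| 150 | 13.0 |
| 180 | 15.7 |
| 200 | 17.4 |
| 230 | 20.0 |
| 250 | 21.7 |

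**One subject, 75 kg, Pb = 230, Pc = 150**

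- Literal volume: 1500 / 230 = 6.52 mL.
- Comparator delivered: 6.52 × 150 = 978 IU, or 978 / 75 = 13.0 IU/kg.
- Shortfall: 1500 − 978 = 522 IU, and 522 / 1500 = 34.8%.
- Correct volume: 1500 / 150 = 10.0 mL.

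**Consistency with the blinding text**

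If both arms used the BPL HRIG potency, subjects of the same weight would receive the same volume in either arm. Volumes would then not differ systematically, contrary to what sections 2.9 and 6.6 expect.

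**Minor: the Appendix F example**

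- It prints the recommended dose per mL where per kg is meant.
- It states 3.4 mL per vial, divides 6.5 by 2.17 and reports 2 vials. In fact 6.5 / 3.4 = 1.91, so 2 vials; 6.5 / 2.17 = 3.00, so 3 vials. The divisor 2.17 equals 500 / 230, the volume holding 500 IU at that potency. One of the two inputs is wrong. The vial count does not alter the 6.5 mL dose.

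**The case against.** The strongest reply is that this is an editorial slip with little practical reach. The sentence just before it fixes 20 IU/kg of comparator. Sections 6.1.2 and 6.3 and Appendix F all point to the right potency, and product selection, volume calculation and syringe volume "will be checked by the unblinded nurse administrator prior to administration to the subject". The pharmacy manual, which is not among the documents, may well be correct. This stands: actual misdosing is unlikely. It does not make the instruction right. The faulty sentence itself refers to the manual, so the manual needs checking, and a second check is only as good as the rule it applies.

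A second reply is that the primary PK population, which also serves the AUC0-7d analysis, requires the full HRIG dose, so under-dosed subjects would drop out. That is not a sure safeguard, because a subject given exactly the volume that Treatment B prescribes could be recorded as fully dosed.

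A third reply is that the illustration sets a nominal comparator potency against an assumed actual BPL HRIG potency and looks mainly at one direction. That is fair. Equal potencies give no error, and a comparator lot of higher potency than BPL HRIG would be over-dosed, which would work against BPL HRIG. The 34.8% is one illustrative case only.

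On the Appendix F vial count, the stated 3.4 mL does agree with the printed 2 vials, which points to 2.17 as the slip. The documents do not confirm it.

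**Conclusion.** The concern holds. Treatment B in Protocol 6.2 names the wrong product's potency and contradicts the comparator dose in its own paragraph, sections 6.1.2 and 6.3, Appendix F and, by implication, sections 2.9 and 6.6. That it was copied from Treatment A is an inference, strongly supported by the identical wording.

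The literal dose is 20 × Pc / Pb IU/kg: between 13.0 and 20.0 IU/kg if the comparator is at its nominal 150 IU/mL and BPL HRIG is between 150 and 230 IU/mL. A comparator lot above or below nominal scales these doses in proportion. Because lot potencies are not given, the real size and direction are unknown. No effect on the Day 14 primary endpoint is claimed. It should still be fixed, because it is a control-arm dosing instruction that is wrong as written.

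**What to change.** In Protocol 6.2, Treatment B, replace the reference to BPL HRIG actual potency with comparator HRIG actual potency, and check that the pharmacy manual uses each product's own lot potency.

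At the same time, correct the dose unit in the Appendix F example to IU/kg and have the sponsor confirm the vial divisor: 3.4 mL gives 2 vials, 2.17 mL gives 3.

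The cost is a few words in section 6.2 and Appendix F plus one check of the manual. No procedures, visits or subjects are added.
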